## 11. DESCRIPTION OF GLOBAL AMENDMENT(S)

### 11.1 GLOBAL AMENDMENT 1

Date of amendment	22 Jul 2020
EudraCT number	NA
EU number	
BI Trial number	1469-0002
BI Investigational Medicinal Product(s)	BI 3011441
Title of protocol	A phase I open-label trial of BI 3011441 in Japanese patients with NRAS/KRAS mutation positive advanced, unresectable or metastatic refractory solid tumours
Global Amendment due to urgent safety reasons	
Global Amendment	x
Section to be changed	Flow chart
Description of change	LVEF measurement added on Day 15 of Cycle 1.  Footnote t) which is explaining hospitalisation period during Cycle 1 and u) which is about additional X-ray were added.
Rationale for change	Based on comment from authority to make sure patient safety.
Section to be changed	Section 3.3.2 and 3.3.4.1
Description of change	Inclusion criteria 13, 14, footnote and treatment discontinuation condition was added to explain more clearly about WOBCP definition and handling for related to pregnancy and nursing.
Rationale for change	Based on comment from authority to be clearer about handling.
Section to be changed	Section 4.1.1
Description of change	Explanation about gelatin used for BI 3011441 was added.
Rationale for change	Based on comment from authority.
Section to be changed	Section 4.1.2 and 5.2.6.3
Description of change	DLT condition for MTD evaluation has updated to avoid underestimate of DLT.
Rationale for change	Based on comment from authority to make sure patient safety.

Section to be changed	Section 5.2.2
Description of change	Measurement of saturation of percutaneous oxygen was added.
Rationale for change	To detect ILD earlier.
Section to be changed	Section 5.2.3
Description of change	Testing for HBV detection was corrected based on local guideline.
Rationale for change	Based on comment from authority to make sure patient safety.
Section to be changed	Section 5.4
Description of change	Additional explanation about disclosure of biomarker analyses result to patient and handling of data and sample after withdrawal were added.
Rationale for change	Based on comment from authority.

## 11.2 GLOBAL AMENDMENT 2

Date of amendment	19 Nov 2020
EudraCT number	NA
EU number	
BI Trial number	1469-0002
BI Investigational Medicinal Product(s)	BI 3011441
Title of protocol	A phase I open-label trial of BI 3011441 in Japanese patients with NRAS/KRAS mutation positive advanced, unresectable or metastatic refractory solid tumours
Global Amendment due to urgent safety reasons	
Global Amendment	x
Section to be changed	Flowchart
Description of change	Footnote h) was updated to increase allowance for ophthalmological assessment.
Rationale for change	Based on comment from principle investigator.
Section to be changed	Section 1.2
Description of change	Drug interaction information was updated based on most recent information. Description of safety information from previous study was updated based on recent IB.
Rationale for change	Same as above

Proprietary confidential information © 2020 Boehringer Ingelheim International GmbH or one or more of its affiliated companies

Section to be changed	Section 1.4.2
Description of change	Description was simplified and moved to Table 1.4.2:1 based on internal consideration
Rationale for change	Same as above
Section to be changed	Section 1.4.3
Description of change	New section about COVID-19 related Benefit-Risk Assessment was added.
Rationale for change	Due to internal requirement
Section to be changed	Section 3.3.3
Description of change	Exclusion criteria 8 was updated to add more detail definition about hypertension.
Rationale for change	To make exclusion criteria clear
Section to be changed	Section 3.3.4.1.1
Description of change	Enrolment stopping rule was updated.
Rationale for change	Due to internal requirement
Section to be changed	Section 4.2.2.1
Description of change	Updated based on recent drug interaction information.
Rationale for change	Same as above
Section to be changed	Table 5.2.3:1
Description of change	Description about myoglobin and creatine kinase was updated.
Rationale for change	Based on request from Risk Management Physician.
Section to be changed	Section 5.2.6
Description of change	DILI definition was updated based on internal process update.
Rationale for change	Due to internal requirement
Section to be changed	Section 5.2.6.2.4
Description of change	Exemptions to AE reporting was updated based on internal process update.
Rationale for change	Due to internal requirement
Section to be changed	Section 5.2.6.3
Description of change	DLT definition about hypertension was updated based to make condition clearer.
Rationale for change	Same as above.

## **12. REFERENCES FOR CTP AUTHORS**

NA

2. LIST OF ABBREVIATIONS

Term	Definition / description
AE	Adverse Event
AESI	Adverse Event of Special Interest
ALCOA	Attributable, Legible, Contemporaneous, Original, Accurate
ALP	Alkaline Phosphatase
ALT	Alanine aminotransferase
ANC	Absolute neutrophil count
AO	Aldehyde oxidase
aPTT	Activated partial thromboplastin
AST	Aspartate transaminase
AUC	Area under the concentration-time curve of the analyte in plasma
BI	Boehringer Ingelheim
BLRM	Bayesian Logistic Regression Model
BRAF	v-Raf murine sarcoma viral oncogene homolog B
CA	Competent Authority
CK	Creatine kinase
CK-MB	Creatine kinase myocardial band
CKD-EPI	Chronic Kidney Disease Epidemiology
C _{max}	Maximum measured concentration of the analyte in plasma
CRA	Clinical Research Associate
CRC	Colorectal cancer
CREE	Enzymatic serum creatinine assay
CREJ	Non IDMS standardised Jaffe
CREJIDMS	Isotype dilution mass spectrometry standardised Jaffe
CRF	Case Report Form
CRO	Contract Research Organisation
CT	Computed Tomography
CT Leader	Clinical Trial Leader
CT Manager	Clinical Trial Manager
CTCAE	Common Terminology Criteria for Adverse Events
CTP	Clinical Trial Protocol

CYP	Cytochrome P450
DCR	Disease Control Rate
DILI	Drug Induced Liver Injury
DLT	Dose limiting toxicity
ECG	Electrocardiography
ECOG	Eastern Cooperative Oncology Group
eDC	Electronic Data Capture
EGFR	Epidermal growth factor receptor
EOR	End of residual effect
EOT	End of Treatment
ERK	Extracellular signal-regulated kinases
EWOC	Escalation with overdose control
FFPE	Formalin-fixed paraffin-embedded
FMO	Flavin-containing monooxygenases
FU	Follow up
GCP	Good Clinical Practice
GMP	Good Manufacturing Practice
HCO ₃	Bicarbonate
IB	Investigator's Brochure
IC50	Inhibitory concentration (50%)
IDMS	Isotype dilution mass spectrometry
IEC	Independent Ethics Committee
IRB	Institutional Review Board
IRT	Interactive Response Technology
ISF	Investigator Site File
KRAS	Kirsten rat sarcoma viral oncogene homologue
LVEF	Left ventricular ejection fraction
MAO	Monoamine oxidases
MAP	Mitogen-activated protein
MAPK	Mitogen-activated protein kinase

MedDRA	Medical Dictionary for Drug Regulatory Activities
MEK	Mitogen-activated protein kinase kinase
MRI	Magnetic resonance imaging
MTD	Maximum tolerated dose
NRAS	Neuroblastoma RAS viral (v-ras) oncogene homolog
NSCLC	Non-small cell lung cancer
OPU	Operative Unit
[REDACTED]	[REDACTED]
p.o.	per os (oral)
[REDACTED]	[REDACTED]
PFS	Progression-free survival
PK	Pharmacokinetics
PK/PD	Pharmacokinetics / Pharmacodynamics
[REDACTED]	[REDACTED]
PT	Prothrombin time
QTcF	QT interval
RAC	Accumulation Index
RAF	Rapidly Accelerated Fibrosarcoma
RAS	Rat sarcoma
RD	recommended dose
[REDACTED]	[REDACTED]
REP	Residual effect period
RPED	Retinal Pigment Epithelial Detachment
[REDACTED]	[REDACTED]
SAE	Serious adverse event
SD	Standard deviation
SMC	Safety Monitoring Committee
SOP	Standard Operating Procedure
[REDACTED]	[REDACTED]
[REDACTED]	[REDACTED]
SUSAR	Suspected unexpected serious adverse reaction
[REDACTED]	[REDACTED]
[REDACTED]	[REDACTED]

TSAP	Trial Statistical Analysis Plan
ULN	Upper limit of normal
WHO	World Health Organisation
β -HCG	beta human chorionic gonadotropin

3. INTRODUCTION

As per ICH E9, the purpose of this document is to provide a more technical and detailed elaboration of the principal features of the analysis described in the protocol, and to include detailed procedures for executing the statistical analysis of the primary and secondary variables and other data.

This TSAP assumes familiarity with the Clinical Trial Protocol (CTP), including Protocol Amendments. In particular, the TSAP is based on the planned analysis specification as written in CTP Section 7 “Statistical Methods and Determination of Sample Size”. Therefore, TSAP readers may consult the CTP for more background information on the trial, e.g., on study objectives, study design and population, treatments, definition of measurements and variables, planning of sample size, and randomisation.

SAS® Version 9.4 will be used for all analyses.

Pharmacokinetics (PK) parameters will be calculated using Phoenix WinNonlinTM software (version 8.1 or higher).

4. CHANGES IN THE PLANNED ANALYSIS OF THE STUDY

This section is not applicable.

5. ENDPOINTS

5.1 PRIMARY ENDPOINT

The primary objective of this trial is to confirm the safety and tolerability of previously identified MTD, BI 3011441 8mg (in Caucasian FIH study) as a single agent when administered orally to adult Japanese patients with NRAS/KRAS mutation positive advanced or metastatic refractory solid tumours.

In this trial, the MTD is an unknown parameter to be determined as the highest dose with less than 25% risk of the true DLT rate being equal to or above 33%. It is estimated by the Bayesian Logistic Regression Model (BLRM), which is specified in CTP Section 7 based on the frequency of patients experiencing dose limiting toxicities (DLTs) during the MTD evaluation period. The MTD is determined by the SMC. For the definition of DLTs, refer to CTP Section 5.2.6.3.

The primary endpoints in this trial are specified in CTP Section 2.1.2; they are

- MTD defined as the highest dose with less than 25% risk of the true DLT rate being equal
- or above 33% during the MTD evaluation period.
- Number of patients with DLTs in the MTD evaluation period.

5.2 SECONDARY ENDPOINTS

5.2.1 Key secondary endpoint

This section is not applicable as no key secondary endpoints have been specified in the protocol.

5.2.2 Secondary endpoints

The secondary endpoints are, as specified in CTP Section 2.1.3:

- Number of patients with DLTs during the entire on-treatment period
- Number of patients with Grade ≥ 3 treatment-related adverse events
- Number of patients with treatment related adverse events at each dose level
- Pharmacokinetic parameters of BI 3011441: $C_{max,ss}$, and $AUC_{0-tz,ss}$

6. GENERAL ANALYSIS DEFINITIONS

6.1 TREATMENT

The trial is an open-label phase I trial with dose escalation, confirmation and expansion of BI 3011441 as monotherapy. For basic study information such as treatments to be administered, assignment of treatment groups, and selection of doses, see CTP Section 4.

For safety analyses, AEs will be classified to one of the following time periods: “Screening”, “On-treatment” or “Follow-up.” This will be applied for all adverse events. Detailed rule for assigning AEs to these time periods are listed below.

- If the date of informed consent \leq AE onset date $<$ date/time of first administration of trial treatment, then the AE is assigned to “Screening”;
- If date of first administration of trial treatment \leq AE onset date \leq date of last administration of trial treatment + 30 days of Residual Effect Period (REP), then the AE is assigned to “On-treatment”;
- If AE onset date $>$ date of last administration of trial treatment + 30 days, then the AE is assigned to “Follow-up”

Table 6.1: 1 Definition of analysis treatment periods for safety analysis

Analysing Treatment Period	Start Date	Stop Date
Screening	Date of informed consent	Date/Time of the first administration of trial treatment
On-treatment	Date of the first administration of trial treatment	Date of the last administration of trial treatment + 30 days of REP
Follow-up	Date of the last administration of trial treatment + 31 days	Date of the last visit
MTD evaluation period*	Date of the first administration of trial treatment	Date of the first administration of trial treatment + 28 days (i.e., treatment cycle)

*The MTD evaluation period is only applied to the patients in the dose escalation part of the trial.

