## 2. TRIAL OBJECTIVES AND ENDPOINTS

### 2.1 MAIN OBJECTIVES, PRIMARY AND SECONDARY ENDPOINTS

#### 2.1.1 Main objectives

The primary objective of this trial is to confirm the safety and tolerability of previously identified MTD, BI 3011441 8mg (in Caucasian FIH study) as a single agent when administered orally to adult Japanese patients with NRAS/KRAS mutation positive advanced or metastatic refractory solid tumours.

The MTD will be determined based on the frequency of patients experiencing DLTs during the MTD evaluation period. The MTD evaluation period is defined as first treatment cycle (28 days). At the end of the dose escalation, the BLRM will be rerun using all DLTs. This result as well as all available data will be used to define the recommended dose (RD).

The secondary objectives is to evaluate the safety and tolerability, and characterise PK of BI 3011441 as monotherapy in Japanese patients with NRAS/KRAS mutation positive advanced solid tumours

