#### 5.2.6.3 Dose limiting toxicities

DLTs will be recorded throughout the trial. Any DLT must be reported to the Sponsor by the Investigator or designee within 24 hours of first knowledge using the same procedure as SAE reporting. Only DLTs occurring in the first 4 weeks (the first cycle) of treatment are considered for dose-escalation decisions made by the SMC. DLTs observed during the MTD

Proprietary confidential information © 2020 Boehringer Ingelheim International GmbH or one or more of its affiliated companies

evaluation period will be considered for MTD determination. In addition, DLT(s) observed during the ophthalmological assessment and echocardiographic assessment of Cycle 2 Day 1 will be considered for MTD determination. However, all AEs and SAEs meeting criteria of DLT observed in all treatment cycles will be considered for determining a RD.

Any of the following AEs will be classified as DLTs if assessed as possibly related to BI 3011441, i.e., unless unequivocally due to underlying malignancy or an extraneous cause and will be reviewed by the SMC.

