6.7 BASELINE, TIME WINDOWS AND CALCULATED VISITS

Unless otherwise specified baseline is defined as the time point closest to but prior to the first administration of any study medication. If no time is specified and the date is the same as the first administration date, then it will still be considered baseline if not specified otherwise. If there is no measurement earlier than the first administration of study medication, then no baseline will be derived.

For laboratory parameters for which not only the examination date but also the sampling time was recorded, examination time should be taken into consideration when defining baseline. That is a laboratory measurement on the same date as the first administration of study treatment is considered as baseline if and only if the examination time of this laboratory measurement is before the first administration of study treatment. If any of these times is missing and the date of laboratory assessment is the same as the date of first administration of study medication, then the laboratory assessment will be considered as according to protocol, i.e., as prior to first study medication.

Study days and visits will be labelled according to the flow charts in the CTP. Study day will be calculated relative to the date of the first administration of study drug. The day prior to first

administration of study drug will be 'Day -1' and the day of first administration of study drug will be 'Day 1'; therefore 'Day 0' will not exist.

Imaging time windows:

Time windows and visits will be calculated to determine the planned day of tumour measurement and response status, based on the protocol-specified tumour imaging schedule.

For the presentation of tumour response data which will follow a calculated visit approach based on the protocol specified tumour imaging schedule: Imaging will be performed at screening and every 8 weeks after the first administration of study treatment (i.e. Week 8, 16, 24 etc.). Image data will be slotted to Week 8, 16, 24 etc. based on their relative study day (from start of treatment) and using a ± 4 week window (e.g., images taken in the first 6 weeks from start of treatment will be assigned to Week 8). If two or more images for a patient are assigned to one interval then the last assessment will be used to ensure PD is not missed.

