7.4 PRIMARY ENDPOINT

7.4.1 Primary analysis of the primary endpoint

For the determination of the MTD, only evaluable patients for MTD in the dose escalation part will be considered (i.e., the MTD set). In this section of the report the data that led to the determination of the MTD are documented and summarised. To be specific, an overall summary of the number of patients with DLTs during the MTD evaluation period (i.e., the first treatment cycle) will be provided for each dose cohort.

The dose escalation and determination of MTD is guided by the BLRM with overdose control specified in CTP Section 7 based on the DLT data in the MTD set. Specifically, estimation of the MTD will be based on the estimation of the posterior probability of the incidence of DLT in toxicity categories during the MTD evaluation period for all evaluable patients for MTD. Tables and bar charts displaying the posterior probabilities of the true DLT rates being in either the under-toxicity interval, the target-toxicity interval or the over-toxicity interval will be produced.

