7.8.1.1 Maximum tolerated dose and dose limiting toxicity

For the determination of MTD in this trial, the following will be evaluated:

- Posterior distribution is based on the number of patients with DLTs with regard to the MTD set and DLTs occurring during the MTD evaluation period (i.e., the first treatment cycle in dose escalation). The toxicity rates for the respective toxicity intervals will be evaluated.
- A table displaying DLTs by primary system organ class and preferred term will be provided by initial treatment for the MTD evaluation period for the MTD Set as well

as for the treated set. The same table will additionally be displayed for all treatment cycles of the on-treatment period for the treated set.

- The purpose of these tables is to summarize and document the data that led to the selection of MTD. A summary of the number of patients with DLT within the MTD evaluation period and for all treatment cycles of the on-treatment period will be given by initial treatment for the treated set.

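### The SAP's DLT window for the MTD model omits the protocol clause that counts Cycle 2 Day 1 eye and echo findings

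*SAP*

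**What the plan says.** **Protocol.** Section 2.1.1: "The MTD evaluation period is defined as first treatment cycle (28 days"). Section 7.3.2 bases the main MTD analysis on DLT data from that period. Section 5.2.6.3 goes further. After stating that DLTs in the evaluation period count, it adds that "DLT(s) observed during the ophthalmological assessment and echocardiographic assessment of Cycle 2 Day 1 will be considered for MTD determination". The same paragraph also says: "Only DLTs occurring in the first 4 weeks (the first cycle) of treatment are considered for dose-escalation decisions made by the SMC".

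**SAP.** Table 6.1:1 ends the MTD evaluation period at "Date of the first administration of trial treatment + 28 days (i.e., treatment cycle"). Section 7.4.1 reports the "number of patients with DLTs during the MTD evaluation period (i.e., the first treatment cycle) will be provided for each dose cohort". Section 7.8.1.1 builds the posterior from "DLTs occurring during the MTD evaluation period (i.e., the first treatment cycle in dose escalation"). Section 6.7 fixes the day count: "the day of first administration of study drug will be 'Day 1'; therefore 'Day 0' will not exist". The Cycle 2 Day 1 clause appears nowhere in the SAP. Section 5.1 points to protocol 5.2.6.3, but only for what a DLT is. Section 4, on changes to the planned analysis, reads: "This section is not applicable".

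**The concern.** Which DLTs count is the sole trial-data input to the Bayesian logistic regression model (BLRM), and so to the primary endpoint. A programmer following the SAP would use a narrower rule than protocol 5.2.6.3, and the error can only go one way, towards fewer DLTs.

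The exposure is mainly ocular:

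- The Flow Chart (footnote h) makes Cycle 2 Visit 1 the first scheduled eye examination on treatment.
- Retinopathy of Grade 2 or higher is a DLT under 5.2.6.3.
- The prior component with weight 0.8 was built from historical data modified to count Grade 2 retinopathy (protocol 7.1). Dropping such events here would put the trial data and the prior on different definitions.

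Echocardiography is less exposed because it is also done on Day 15. However, an LVEF fall becomes a DLT only after drug is held and a follow-up echo is obtained. A fall first seen at Cycle 2 Day 1 would therefore normally be confirmed after Day 29, and neither document says which date governs.

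Amendment 1 states that the DLT condition for MTD evaluation (sections 4.1.2 and 5.2.6.3) was updated so that DLTs would not be underestimated. It does not name the sentence, but the SAP window works against that aim.

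**Working it through.** **1. Dates.** Inputs: first dose is Day 1 (SAP 6.7); cycles last 28 days; Cycle 2 Visit 1 has a ±2-day window (Flow Chart); the eye examination may be a further ±2 days from the visit (footnote h).

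- First dose + 28 days = Day 1 + 28 = Day 29.
- A 28-day first cycle = Days 1 to 28.
- Cycle 2 Visit 1 = Day 29 ± 2 = Days 27 to 31.
- Eye examination = Days 27 − 2 to 31 + 2 = Days 25 to 33, taking footnote h's allowance from the actual visit.

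| Finding first dated | Protocol 5.2.6.3 | SAP, + 28 days inclusive | SAP, 28-day cycle |
|---|---|---|---|
| To Day 28 | counts | counts | counts |
| Day 29 | counts | counts | lost |
| Days 30–31 (eye: to 33) | counts | lost | lost |

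**2. Reproducing the model.** logit(π_d) = log α + β·log(d/8), with the three-component prior of protocol Table 7.1:2, integrated on a two-dimensional grid. A dose is admissible under overdose control (EWOC) if P(π_d ≥ 0.33 | data) < 0.25. The prior overdose probabilities at 4, 6, 7 and 8 mg come out at 0.129, 0.232, 0.310 and 0.422; Table 7.1:3 prints 0.128, 0.233, 0.310 and 0.422.

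**3. Effect of one uncounted DLT at 8 mg.** Data: 0/3 at 4 mg, 0/3 at 6 mg, x/6 at 8 mg.

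| x | P(overdose) at 8 mg, recomputed | Printed (scenarios 19–22) | Highest dose meeting EWOC |
|---|---|---|---|
| 0 | 0.023 | 0.023 | 8 mg |
| 1 | 0.103 | 0.106 | 8 mg |
| 2 | 0.268 | 0.274 | 7 mg |
| 3 | 0.502 | 0.501 | 7 mg |
| 4 | 0.737 | – | 6 mg |
| 5 | 0.903 | – | 6 mg |

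Removing one DLT raises the admissible dose when the true count is 2/6 (7 to 8 mg) or 4/6 (6 to 7 mg), but not at 1/6, 3/6 or 5/6.

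**4. One-DLT steps in protocol Table 10.2:1.** These compare printed scenario pairs that differ by one DLT at the stated dose.

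- At 8 mg there are 14 pairs: 16–17, 17–18, 19–20, 20–21, 21–22, 32–33, 34–35, 35–36, 37–38, 39–40, 40–41, 42–43, 44–45, 45–46. Dropping one DLT changes the recommended dose in two. Scenario 18 becomes 17 (P(overdose) 0.500 to 0.234) and scenario 21 becomes 20 (0.274 to 0.106); both move from 7 to 8 mg. The other 12 are unchanged.
- At 6 mg there are six pairs: 6–7, 8–9, 9–10, 10–11, 12–13, 14–15. All but 10–11 change, so 5 of 6.

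**The case against.** The strongest reply is that the SAP follows its source. It says it is based on protocol section 7, and 7.3.2 together with 2.1.1 confines the MTD analysis to the 28-day period. On that view the conflict lies inside the protocol, and the SAP's statement of no changes is accurate against section 7. This stands as to cause, and it is why the protocol needs correcting too. It does not make the SAP consistent with 5.2.6.3.

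Second, the SAP's only dated rule ends on Day 29 and so captures every on-schedule finding. Protocol 4.1.4.1 also requires a scheduled eye examination to be clear before a new cycle starts. That favours timely examination, and a finding that blocks Cycle 2 arguably still belongs to Cycle 1. This narrows the loss. But the SAP twice glosses the period as the first treatment cycle, and 5.2.6.3 treats Cycle 2 Day 1 findings as additional to the period, so the boundary remains unclear.

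Third, the Safety Monitoring Committee (SMC) determines the MTD, sees data beyond the evaluation period, and receives DLT reports quickly. Late DLTs also reach the recommended-dose decision and the all-cycle tables, and an event with an earlier recorded onset may still count. These are real safeguards, but none corrects the model input or the reported primary analysis.

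Fourth, the step counts come from illustrative scenarios and are not frequencies. In cohorts of three, 4/6 at 8 mg is hard to reach, because 2/3 already triggers a step down; 2/6 against 1/6 is the realistic case. That is correct.

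Finally, the two sentences of 5.2.6.3 on escalation and on the MTD may be a deliberate two-tier rule. If so, the protocol should say so.

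**Conclusion.** The concern holds. As written, the SAP excludes from the MTD model some DLTs that protocol 5.2.6.3 counts: those first dated after Day 29 on either reading, and those on Day 29 itself if the 28-day cycle governs. The omission is shared with protocol 2.1.1 and 7.3.2.

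The textual mismatch is certain. Its practical effect is conditional: the documents give no basis for estimating how often a finding would fall in the gap, and it may never happen. If one does, the recommended dose may or may not move, as the 8 mg and 6 mg comparisons show. The 2/6 against 1/6 case matters most, because it decides between 7 mg and 8 mg and 8 mg is the dose the trial sets out to confirm. The Day 33 limit assumes that the eye-examination allowance runs from the actual visit date. This should be fixed before the MTD analysis is run.

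**What to change.** - **SAP Table 6.1:1, 7.4.1 and 7.8.1.1:** state that the MTD analysis uses first-cycle DLTs plus DLTs observed at the Cycle 2 Day 1 ophthalmological and echocardiographic assessments, whatever their actual date. State whether the period itself ends on Day 28 or Day 29.
- **Dating rule:** say how an LVEF fall first seen at the Cycle 2 Day 1 echo, but confirmed as a DLT later, is dated for this analysis.
- **Protocol 2.1.1 and 7.3.2:** reconcile with 5.2.6.3.
- **Protocol 5.2.6.3:** reconcile, or explicitly distinguish, the sentence on DLTs for escalation decisions and the sentence on DLTs for MTD determination. Which escalation rule applies is for the sponsor to decide.

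The cost is SAP wording, one derivation flag and a few clarifying protocol sentences. The MTD model run may have to wait a few days for the Cycle 2 Day 1 results.
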